8.1.6 Prior Treatment Details

The investigator or qualified designee will review all prior cancer treatments including systemic treatments, radiation, and surgeries.

8.1.7 Assignment of Patient Number

Patients will be assigned a Patient Number upon consent.

8.2 Clinical Procedures/Assessments

The following clinical assessments should be performed in accordance with the Study Calendar (Section 7.0).

8.2.1 Adverse Event (AE) Monitoring

The investigator or qualified designee will assess each subject to evaluate for potential new or worsening AEs. Adverse experiences will be graded and recorded throughout the study according to NCI CTCAE Version 5.03. Toxicities will be characterized in terms regarding seriousness, causality, toxicity grading, and action taken regarding investigational treatment.

Please refer to Section 8.6 for detailed information regarding the assessment and recording of AEs. AE monitoring may occur more frequently than required as clinically indicated.

8.2.2 Concomitant Medications Review

The investigator or qualified designee will review prior medication use, including any protocol-specified washout requirement.

8.2.3 Full Physical Exam

The investigator or qualified designee will perform a complete physical exam. Clinically significant abnormal findings should be recorded as medical history.

8.2.4 Directed Physical Exam

For timepoints that do not require a full physical exam, the investigator or qualified designee will perform a directed physical exam as clinically indicated prior to study treatment administration.

8.2.5 Vital Signs

The investigator or qualified designee will measure and record vital signs, including temperature, pulse, respiratory rate, weight, and blood pressure.

8.2.6 ECOG Performance Status

The investigator or qualified designee will assess ECOG Performance Status (see Section 9.4).

8.2.7 Radiographic Disease/Response Assessment

Radiographic assessments of measurable disease will be performed using CT imaging with IV contrast. CT scans should encompass at least the chest and abdomen. CT pelvis should be included according to usual clinical practice. RECIST 1.1 criteria will be used to assess response to therapy. Radiographic imaging will be performed every 6 weeks (42 +/- 7 days). After completion of 24 weeks of study treatment, the interval between radiographic evaluations can be extended to up to 9 weeks +/- 7 days, according to the discretion of the investigator. For patients who are known to have CNS disease at the time of enrollment, CNS imaging should be performed during study participation according to usual clinical practice.

8.2.7.1 Isolated Central Nervous System Progression

Isolated CNS progression does not require discontinuation of study treatment. Bomedemstat should be held for seven days prior to until seven days following the administration of CNS-directed therapy (e.g. a standard course of whole brain radiotherapy or stereotactic radiosurgery, in accordance with institutional practice). The subject may then resume study therapy when clinically appropriate. If more than 4 weeks have elapsed since the previous dose of study drug, the subject should undergo a radiographic disease assessment before restarting study treatment.

8.2.7.2 Treatment Beyond Initial Determination of Progression

If a subject has unconfirmed PD (Section 9.2.4) and is clinically stable and without symptomatic deterioration (Section 9.2.6), it is at the discretion of the Investigator to continue study treatment per protocol until PD is confirmed (Section 9.2.4). For subjects with new lesions, the diameters of the new lesions will be recorded.

Clinically stable is defined as:

1. Absence of symptoms and signs indicating clinically significant PD (including worsening of laboratory values).
2. Absence of rapid progression of disease or progressive tumor at critical anatomical sites (eg, cord compression) requiring urgent alternative medical intervention.

Upon confirmation of PD (Section 9.2.4) or onset of symptomatic deterioration / loss of clinical stability, study treatment should be discontinued. Administration of study treatment beyond confirmed progression is not permitted.

8.2.8 *Tumor Tissue Collection and Correlative Studies Blood Sampling*

Archival tumor tissue (defined as 10-15 serial sections, each 4 microns thick, mounted onto positively charged glass slides, or a block) will be requested as part of study participation. However, adequate archival tissue is not a requirement for study participation. Archival tissue samples will be tested for immunohistochemical expression studies of key markers which may include PD-L1, ASCL1, ATOH1, NEUROD1, POU2F3, REST, and YAP1.

Peripheral blood samples for correlative research studies should be collected in two to three 10 mL lavender top (EDTA) or Streck cfDNA tubes (~20-30 mL per collection). Research blood collections will be performed for correlative research studies at the following timepoints: during screening, at every radiographic assessment, and at end of treatment visit, regardless of whether radiographic assessment was performed. If radiographic assessment intervals are extended due to durable clinical benefit, research blood collection intervals will be extended to match.

Correlative studies will be performed in the [name] lab at the Fred Hutchinson Cancer Center in Seattle, WA. Correlative studies will include isolation of circulating tumor cells for multi-omic analysis (e.g. measurements of DNA alterations, mRNA transcript levels, and protein abundance) and the generation of patient-derived xenograft models, to isolate circulating free DNA (cfDNA) for multidimensional analysis (e.g. DNA alterations, fragmentation patterns), and to isolate genomic DNA from peripheral blood mononuclear cells for more accurate identification of somatic mutations. The goal of correlative studies is to identify predictors of clinical benefit from bomedemstat in combination with atezolizumab.

8.3 Laboratory Procedures/Assessments

Details regarding specific laboratory procedures/assessments to be performed in this study are provided below.

Version 3.0 August 08, 2022

Page 30 of 47

8.3.1 Laboratory Safety Evaluations (Hematology, Chemistry and Urinalysis)

Laboratory tests for hematology, chemistry, urinalysis, and others are specified in Table 8.1. Results must be reviewed by the investigator or qualified designee and found to be acceptable prior to initiation of the next cycle of study treatment.

Table 8.1. Laboratory tests.

CBC w/ Diff	Complete serum chemistry panel	Other
Hematocrit	Alanine aminotransferase (ALT)	Activated partial thromboplastin time (aPTT)
Hemoglobin	Albumin	Cortisol, serum
Platelet count	Alkaline phosphatase	Prothrombin time (PT/INR)
White blood cell count (total)	Aspartate aminotransferase (AST)	Serum beta-human chorionic gonadotropin (β -hCG) (required if urine test is inconclusive)
Red blood cell count	Bilirubin, Total	Thyroid stimulating hormone (TSH)
Absolute neutrophil count	Blood Urea Nitrogen	Thyroxine, free (FT4)
	Carbon dioxide (CO ₂ or Bicarbonate)	Urine pregnancy test (only for women of childbearing potential)
	Chloride	Blood for correlative studies
	Creatinine	
	Glucose	
	Potassium	
	Protein, Total	
	Sodium	

8.4 Other Procedures

8.4.1 Treatment Discontinuation or Subject Withdrawal

When a subject discontinues study treatment permanently or withdraws prior to trial completion, all applicable activities should be performed at the time of discontinuation (Section 7.0). Any adverse events which are present at the time of discontinuation/withdrawal should be followed in accordance with the safety requirements outlined in Section 8.6. An End of Treatment visit (Section 8.5.3.1) should be performed within 7 days. If the subject has not experienced disease progression (see Section 8.2.7) and has not withdrawn from the study, the subject should undergo regular Monitoring visits (Section 8.5.3.3) for disease assessment according to the Study Calendar (Section 7.0).

8.5 Visit Requirements

Visit requirements are outlined in the Study Calendar (Section 7.0). Specific procedure-related details are provided above in Clinical Procedures/Assessments (Section 8.2).

8.5.1 Screening Period

The following assessments will be performed up to 14 days prior to Cycle 1 Day 1:

1. Full Physical Examination
2. Vital Signs and weight
3. ECOG Performance Status
4. Pregnancy test or Serum β -HCG in females of childbearing potential
5. CBC w/ Diff
6. PT/INR and aPTT
7. Comprehensive serum chemistry panel
8. Archival tissue collection, if available
9. Radiographic disease assessment (see Section 8.2.7).
 - a. CT with IV contrast of the chest and abdomen. CT pelvis should be included according to usual clinical practice. For patients known to have CNS disease, CNS imaging should be performed according to usual clinical practice.
10. Blood for correlative studies

8.5.2 On Treatment Period

The following assessments will be performed at On Treatment Period visits as identified in the Study Calendar (Section 7.0). Specific procedure-related details are provided above in Clinical Procedures/Assessments (Section 8.2).

1. Adverse event review
2. Concomitant medication review
3. Directed physical examination
4. Vital signs and weight
5. ECOG performance status
6. CBC with differential
7. Comprehensive serum chemistry panel
8. TSH, FT4, and random serum cortisol
9. Radiographic disease/response assessment (see Section 8.2.7)

10. Blood for correlative studies (see Section 8.2.8)

8.5.3 Off Treatment Visits

8.5.3.1 End of Treatment Visit

The mandatory End of Treatment visit should be conducted at the time of permanent study treatment discontinuation, or within 7 days thereafter, unless the patient is unable to participate in the visit.

8.5.3.2 Safety Follow-Up Visit

The mandatory Safety Follow-Up Visit should be conducted approximately 30 days after cessation of study treatment, or before the initiation of a new anti-cancer treatment outside the confines of this study, whichever comes first, unless the patient is unable to participate in the visit. All AEs that occur prior to the Safety Follow-Up Visit should be recorded.

8.5.3.3 Monitoring

Subjects who discontinue study treatment for a reason other than disease progression or withdrawal from study move into the monitoring phase and should be assessed radiographically every 8 weeks (56 ± 7 days) as in Section 8.2.7 to monitor disease status. Every effort will be made to collect information regarding disease status until the start of new anti-neoplastic therapy, disease progression, death, or end of the study. Information regarding post-study anti-neoplastic treatment will be collected if new treatment is initiated.

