Radiographic disease response assessments will occur every 6 weeks +/- 7 days (after completion of 24 weeks of study treatment, the interval can be extended to every 9 weeks +/- 7 days at the discretion of the investigator) for the duration of study participation with disposition based on the results as follows:

1. Subjects who experience disease response (CR or PR) or stable disease without evidence of clinical deterioration will continue bomedemstat and atezolizumab maintenance therapy. Absence of clinical deterioration is determined by the treating physician and is defined as follows:

- a. Absence of signs and symptoms of disease progression.
- b. Absence of rapid disease progression.
- c. Absence of progressive tumor at critical anatomical sites (e.g. cord compression) requiring urgent alternative medical intervention.

2. Subjects who experience disease progression that is isolated to the CNS are eligible to continue study treatment following definitive therapy to the CNS disease, provided that ongoing study treatment is likely to provide additional benefit to the patient, at the discretion of the investigator and after appropriate discussion with the patient. See Section 8.2.7.1 for further details.
3. Subjects who experience confirmed disease progression by RECIST 1.1 (other than isolated CNS progression) and/or clinical deterioration should discontinue study treatment (see Section 6.6.1).

Note: Subjects with unconfirmed disease progression by RECIST 1.1 who do not have evidence of clinical deterioration may continue to receive study treatment, at the discretion of the investigator and after appropriate discussion with the patient. Subjects should be monitored closely and a follow-up scan should be performed after 28 days, or sooner if clinical deterioration occurs. If the follow-up scan confirms disease progression, the subject should discontinue study treatment. See Section 8.2.7.2 for further details.

Subjects will be followed closely until disease progression per RECIST 1.1 or initiation of new anticancer treatment, whichever occurs first; and will afterwards be followed for survival until death or study termination, whichever occurs first. Blood samples for biomarker assessments will be collected at protocol-defined timepoints to support study endpoints.

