10.3 Sample Size Justification and Analysis Plans

The total accrual goal to this study is 34 eligible patients. Based on the IMPOWER133 study, we estimate that 35% of patients with ES-SCLC are alive and free from disease progression at 6 months after initiation of maintenance anti-PD(L)1 therapy. With 34 patients, this study design has 90% power to detect a 25% improvement in 6-month PFS rates (from 35 to 60%) using a 1-sided binomial test at the 5% level. The observation of 17 patients progression-free (i.e. alive without PD or symptomatic deterioration) at 6 months (a 50% rate) would be considered evidence to rule out a 35% 6-month PFS rate. With 34 patients, proportions can be estimated to within 17% with 95% confidence and any toxicity with at least 10% prevalence is likely to be observed with 97% confidence.

Additional analyses will evaluate proportions (such as toxicity or response rates within subgroups) accompanied by 95% confidence intervals. Distributions for time-to-event outcomes (PFS, OS) will be evaluated using the method of Kaplan-Meier. For point estimates at landmark times, the associated 95%

confidence interval (CI) will be calculated using Greenwood's formula and based on a log-log transformation applied on the survival function.

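### Patients who stop treatment without progression move from 6-weekly to 8-weekly scans, against Sections 6.1 and 8.2.7 and with no stated anchor, so before week 24 their progression is on average dated later

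*Combined protocol and SAP*

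**What the plan says.** **Six weeks.** Section 6.1: "Radiographic disease response assessments will occur every 6 weeks +/- 7 days", with an optional 9-week interval after 24 weeks of study treatment, "for the duration of study participation with disposition based on the results as follows". Section 8.2.7 agrees: "Radiographic imaging will be performed every 6 weeks (42 +/- 7 days"), with the same later option. Footnote 5 of the Study Calendar (Section 7.0) also gives 6 weeks, and it is attached to the disease-assessment entry in the Monitoring column as well as to the on-treatment entry.

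**Eight weeks.** Section 8.5.3.3, for patients who stop for a reason other than progression or withdrawal: they "should be assessed radiographically every 8 weeks", given there as 56 ± 7 days and with a reference to Section 8.2.7. The Calendar's Monitoring column is headed with an 8-week interval.

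**At discontinuation.** Section 8.5.3.1: "The mandatory End of Treatment visit should be conducted at the time of permanent study treatment discontinuation, or within 7 days thereafter". It asks for no scan. The Calendar's disease-assessment row is blank under End of Treatment, and Section 8.2.8 takes research blood at that visit whether or not imaging was done.

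**Use of the scans.** Section 9.6 dates PFS at the first documentation of progression, at symptomatic deterioration or at death, and censors at last contact. Section 10.3 counts patients progression-free at 6 months and adds Kaplan-Meier estimates of PFS.

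**The concern.** Patients in Monitoring are still in the study. Sections 6.6 and 8.4.1 keep them under disease assessment until progression or new therapy. Sections 6.1 and 8.2.7 and footnote 5 therefore give these patients one interval, and Section 8.5.3.3 and the Calendar column give another. Section 8.5.3.3 also contradicts the section it cites.

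For the analysis, the frequency of looking for progression depends on a post-baseline event, stopping treatment. A scan-detected event can be dated no earlier than the scan that shows it. Because censoring is at last contact and not at last adequate scan, a patient who has been seen but not scanned still accrues progression-free time. With a single arm there is no control group in which the same delay would cancel. Both the 6-month count and the Kaplan-Meier curve use these dates.

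**Working it through.** **1. The plan's own figure.** Section 10.3 gives n = 34, 35% versus 60%, a one-sided 5% binomial test, success at 17, and 90% power. Exact binomial: P(X ≥ 17 | 34, 0.60) = 0.913, so the stated power is reproduced. P(X ≥ 17 | 34, 0.35) = 0.0514, the baseline for step 5.

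**2. Gap between consecutive scans before week 24.** Let s be the weeks since the last scan when treatment stops, with 0 ≤ s < 6.

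| Situation | Nominal gap |
|---|---|
| On treatment | 6 weeks |
| 8 weeks counted from last scan | 8 weeks |
| 8 weeks counted from discontinuation | s + 8, i.e. 8 to 14 weeks; mean 3 + 8 = 11 if s is uniform |

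With every window used late, the extreme is (42 + 7) + (56 + 7) = 112 days = 16 weeks.

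**3. Dating delay.** If progression is equally likely at any point between two scans, the mean delay is half the gap: 6/2 = 3 weeks on treatment, against 8/2 = 4, 11/2 = 5.5, or 14/2 = 7 at the extreme. The excess is 1, 2.5 or 4 weeks per affected patient. Averaged over the cohort:

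- 3 affected: 3/34 × 1 = 0.09, 3/34 × 2.5 = 0.22, 3/34 × 4 = 0.35 week.
- 7 affected: 7/34 × 1 = 0.21, 7/34 × 2.5 = 0.51, 7/34 × 4 = 0.82 week.

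The 3 comes from Section 10.2.2, which ends the study at the fourth permanent stop for unacceptable toxicity. The 7 is an assumption, about 20% of 34 stopping for any non-progression reason; the documents give no such figure.

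**4. Last scan before 6 months (week 26).** Under 6-weekly scanning it is week 24. Counted from discontinuation, it falls between weeks 18 and 26 (mean 21.3 for a stop time uniform over weeks 0 to 24). It is week 18 for anyone stopping between weeks 18 and 24, who loses the week-24 scan. Counted from the last scan, it is week 20, 22, 24 or 26.

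**5. Effect on the 17-of-34 criterion.** Assumptions: exponential PFS, every event found by scan, and a null rate of 35% as seen at the week-24 scan, so S(t) = 0.35^(t/24).

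- Last scan at week 18: S(18) = 0.35^0.75 = 0.455.
- Last scan at week 20 (the earliest under the last-scan anchor): S(20) = 0.35^(20/24) = 0.417.
- With k affected patients, the count is the sum of Bin(34 − k, 0.35) and Bin(k, S). For k = 3 and S = 0.455 the overall rate is (31 × 0.35 + 3 × 0.455)/34 = 0.359.

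| Affected patients | P(17 or more), all last scanned at week 18 | P(17 or more), all at week 20 |
|---|---|---|
| 0 | 0.051 | 0.051 |
| 1 | 0.055 | 0.054 |
| 3 | 0.064 | 0.060 |
| 7 | 0.086 | 0.072 |

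**6. Sensitivity.** Step 5 treats affected patients as a random draw. Someone who stops in weeks 18 to 24 without progression has already passed the week-18 scan. Such a patient's chance of passing a week-24 scan is 0.35/0.455 = 0.769, and it becomes 1 if that scan is lost. To keep the overall null at 35%, the other 31 patients have rate (34 × 0.35 − 3 × 0.769)/31 = 0.309. P(17 or more) then goes from 0.045 to 0.068 for k = 3. For k = 7 the others have rate (34 × 0.35 − 7 × 0.769)/27 = 0.241, and it goes from 0.035 to 0.093. The order of size is the same.

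**The case against.** The best defence is that the 6.1 sentence sits in an overview and leads into dispositions that mostly decide whether treatment continues, so it can be read as an on-treatment schedule. The 8-week rule appears in both 8.5.3.3 and the Calendar column, and sites could follow it. The interval may well be deliberate. What this does not remove is the wording of 6.1 on duration, the citation of 8.2.7 by a section that departs from it, the 6-week footnote on the Monitoring entry, and the missing anchor.

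Three stronger readings might be inferred, and the documents do not support them.

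- *Gaps of 14 to 16 weeks are typical.* They are the extreme of one of two possible anchors. The other gives 8 weeks.
- *The bias falls mainly on patients who tolerated bomedemstat worst.* Section 10.2.2 limits permanent stops for unacceptable toxicity to 3 in a completed study, and Section 10.2.1 ends the study at one encephalopathy. Noncompliance, intercurrent illness, investigator decision, and more than three down-titrations or holds lead to the same schedule. No PFS analysis by tolerability is planned.
- *PFS is always inflated.* After week 24, 8-weekly scanning can be tighter than the optional 9-weekly. Before then, an individual patient's scan may by chance fall close to week 26.

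It also stands that symptomatic deterioration and death are PFS events, and that off-treatment patients have examination visits. Some events will therefore be recorded without waiting for a scan.

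**Conclusion.** The point holds as an unreconciled scan schedule with a modest effect. Before week 24, a patient who stops for any non-progression reason has a nominal gap of 8 weeks, or of 8 to 14 weeks, against 6 on treatment. Which applies depends on an anchor that the plan does not state. On average progression is dated later in these patients, in the period that decides the 6-month endpoint.

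The cohort-average shift is below one week in every case examined. The rise in the false-positive chance, from 0.051 to 0.064 with 3 affected patients or 0.086 with 7, is an upper-end illustration. It assumes that every affected patient missed the week-24 scan and that no event was detected clinically. The criterion already sits slightly above 5%, so it has no slack to absorb even a small increase. This does not invalidate the primary endpoint, but it is an avoidable source of favourable bias and worth correcting.

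**What to change.** Reconcile Sections 6.1, 8.2.7 and 8.5.3.3, the Calendar's Monitoring column and footnote 5 to one scan schedule counted from Cycle 1 Day 1 regardless of treatment status: every 6 weeks through week 24, with the optional 9-week interval afterwards. Tie that option to 24 weeks from Cycle 1 Day 1. As worded, it depends on completing 24 weeks of treatment, which early stoppers never do. A fixed calendar also settles the anchor, and a scan due around discontinuation is still done without a separate End of Treatment scan.

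The cost is amendment wording and, for a patient who stops early, about one extra CT in the first 24 weeks (24/6 = 4 scans against 24/8 = 3). After week 24 this is partly offset where the 9-week interval replaces the 8-week one. With all patients on the 6-week grid up to the landmark, the last scan before week 26 is nominally week 24 for everyone, and the 17-of-34 criterion keeps its exact level of 0.0514 and power of 0.913.

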8.5.3.4 Survival Follow-up

Once a subject is no longer eligible for study treatment due to disease progression or starts a new anti-cancer therapy outside the confines of this study, the subject moves into the survival follow-up phase. Survival status of the subject will be ascertained every 12 weeks, via medical records or by directly contacting the patient, until death, withdrawal of consent, or the end of the study, whichever occurs first. Three attempts to contact a subject should be made before the subject is considered lost to follow up.

